An asthma exacerbation that occurs  $\leq$  7 days of the last dose of systemic steroids, prescribed for a prior exacerbation, will be counted as the same exacerbation event.

Subjects who experience an exacerbation during the run-in period should be screen failed and may be considered for re-screening. Discontinuation due to an exacerbation after randomization (Visit 3c) is not mandatory and subjects may remain on the investigative product at PI's discretion. A stable period of 6 weeks is recommended between the last dose of systemic steroids for treating an asthma exacerbation and the EOT bronchoscopy. For such subjects, the timing of EOT bronchoscopy assessments should be discussed and agreed upon with AstraZeneca study physician.

Reasonable attempts should be made by the Investigator to bring the subject into the study centre for evaluation of a diary alert or subject initiated asthma worsening, particularly when it results in additional treatment being prescribed. Study centre evaluations for asthma worsening may occur as an unscheduled (UNS) visit or as part of an ordinary centre visit if the worsening happens to be coincident with a scheduled visit window. A copy of the medical record should be obtained for exacerbations evaluated and treated at non-study centres (e.g., by the primary care HCP or at an ED/hospital) and details entered into the exacerbation eCRF (EXACA module) in a timely fashion. Changes in concomitant medication due to an exacerbation must be recorded in the appropriate module of the eCRF.

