## 8.5.5 Sensitivity analysis

For the primary and secondary variables, non-parametric analysis methods will be applied as sensitivity analyses.

It is likely that some biopsy specimens will not be evaluable. Also, due to the invasive procedures performed, it is likely that some subjects will withdraw from the study. We cannot rule out that there is a relationship between unobserved values and the likelihood of data being missing and therefore the effect of missing data will be assessed using multiple imputations and a range of assumptions for the missing data.

Full details of the sensitivity analyses will be pre-specified in SAP and documented prior to database lock of the studies.

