It is likely that some biopsy specimens will not be evaluable. Although some subjects will have missing data for other reasons, it is envisaged that the invasive nature of the biopsy procedure will directly result in some missing biopsy outcomes. Such biopsy-related missing pattern is likely not to be informative about the potential outcome – that is, such data is likely to be missing at random (MAR). The following sensitivity analysis for the primary and the secondary endpoints will be used to explore the robustness of the analyses to assumptions about this missing biopsy data. This sensitivity analysis will take account of the potential difference between biopsy-related missingness (arguably MAR) and other sources of missing data. A subject will be counted as having biopsy-related missing outcome if the biopsy outcome is missing at Week 12, but other Week 12 data was collected for the subject. In the sensitivity analysis implemented by multiple imputation (MI), biopsy-related missingness will be imputed assuming MAR. All other missing values will be imputed with the"Dropout Reason-based Multiple Imputation (DRMI)": Missing counts will be imputed differently depending on the reason for dropout; counts for subjects in the Tralokinumab arms who dropped out for a treatment related reason are imputed based on the expected event rate in the placebo arm  $(p_{T2} = p_{P1})$ , whereas the remaining subjects who have dropped out are imputed assuming MAR. Treatment related reasons include (1) AEs, (2) Death (3) development of study specified reasons to stop active treatments and (4) severe non compliance.

The data will be log-transformed before the imputation process begins, and the ratio of each scheduled visit to baseline visit will be the variable of interest for imputation. The missing ratio at Week 12 (Visit 9) will be imputed using regression imputation (using MONOTONE REG option of SAS PROC MI). 100 imputations will be carried out, and a seed of 221014 will be used. The analysis of each of the imputed datasets will be as described for the primary

analysis in Section 4.2.4 and these will be combined using SAS procedure PROC MIANALYZE and results presented as per the primary analysis.

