This approach assumes that no subject has a missing baseline result. If there are subjects with missing baseline results, a regression imputation will be used first, with missing baselines being replaced by their predicted values, given the other baseline covariates (apart from treatment group).

A further sensitivity analysis of the primary efficacy analysis will be done removing the subjects who have a subject with a baseline value=0 or a week 12=0.

As per section 3.1.4, week 12 records not collected within study days 78-99 will not be analyzed as part of the primary efficacy. A further sensitivity analysis of the primary efficacy will be done keeping the subjects with the week 12 records falling outside of the week 12 window.

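### Does the multiple imputation mishandle Week 12 biopsies pushed past day 99 by the steroid-free interval?

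*SAP*

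**What the plan says.** Protocol 5.1.12 allows a subject who has an exacerbation after randomisation to stay on investigational product. It then advises: "A stable period of 6 weeks is recommended between the last dose of systemic steroids for treating an asthma exacerbation and the EOT bronchoscopy". For these subjects "the timing of EOT bronchoscopy assessments should be discussed and agreed upon with AstraZeneca study physician". No latest date is given.

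SAP 3.1.4 (Table 1) sets the Week 12 analysis window at study days 78 to 99, with randomisation as day 1, and treats an empty window as missing. SAP 4.1.1 applies this to the primary endpoint: "week 12 records not collected within study days 78-99 will not be analyzed as part of the primary efficacy". Its next sentence plans a further analysis of the primary endpoint, "keeping the subjects with the week 12 records falling outside of the week 12 window".

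The multiple imputation in SAP 4.1.1 has two parts. A subject with a "biopsy-related missing outcome if the biopsy outcome is missing at Week 12, but other Week 12 data was collected for the subject" is imputed under MAR. The reason given is that the procedure is invasive: "Such biopsy-related missing pattern is likely not to be informative about the potential outcome". All other missing values are handled by reason for dropout. Tralokinumab subjects who left for a treatment-related reason are imputed from placebo; the other dropouts are imputed under MAR.

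Protocol 8.5.5 is more cautious: "We cannot rule out that there is a relationship between unobserved values and the likelihood of data being missing". It promises to assess the effect with "multiple imputations and a range of assumptions for the missing data".

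**The concern.** A biopsy delayed by steroid treatment is not a failed procedure. Its cause is an exacerbation, which may be related both to airway eosinophils and to treatment arm. If it falls after day 99 while other Week 12 assessments were done on time, the SAP's definition puts the subject with the failed biopsies and uses MAR, on a rationale written for something else. The subject has not dropped out, so the placebo-based rule does not apply. The SAP does not name the steroid cause, and it plans no count by arm of biopsies delayed in this way.

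At stake would be a sensitivity analysis that looks like a test of informative missingness but tests nothing for these subjects, and a reader unable to see whether their exclusion from the primary analysis is balanced.

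**Working it through.** **The plan's own figure.** Protocol 8.2 gives log-scale SDs of 1.62 and 1.82, a 3.5-fold effect and 31 evaluable subjects per arm. The root mean square SD is sqrt((1.62² + 1.82²)/2) = 1.723 and ln 3.5 = 1.253. With the noncentral t distribution, power is 79.1% at 30 per arm and 80.4% at 31, so 31 reproduces. The standard error is 1.723 × sqrt(2/31) = 0.438. The smallest significant ratio is exp(2.000 × 0.438) = 2.40, as stated. The same factor is the half-width of the 95% confidence interval on the ratio scale.

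**Day arithmetic.** Six weeks is 42 days and 99 − 42 = 57. A last steroid dose on day 57 or earlier still allows a biopsy by day 99. A last dose on days 58 to 85 puts the earliest biopsy that follows the advice on days 100 to 127, outside the window. The displacement is real.

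**Tracing the rules.**
- If the other Week 12 data are collected on time, the subject is in the biopsy-related class: MAR.
- If the whole end-of-treatment visit moves (protocol 5.1.12 does not say whether it does), the subject leaves that class. There is no treatment-related dropout reason, so the nearest rule is again MAR.
- In either case, a late biopsy that was taken enters the out-of-window analysis with its observed value.

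The label therefore does not determine how these subjects are imputed.

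**How many.** The documents give no on-study rate; protocol 3.2 only excludes subjects with more than three steroid-treated exacerbations in the previous year. Assume a constant rate r per year, full adherence to the advice, and Visit 9 on day 85. There are then 28 risk days (58 to 85) and p = 1 − exp(−r × 28/365.25).

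| Assumed r | p | Of 31 per arm | Bound on a 3.5-fold effect |
|---|---|---|---|
| 0.5 | 3.8% | 1.2 | 3.34 |
| 1 | 7.4% | 2.3 | 3.19 |
| 2 | 14.2% | 4.4 | 2.93 |

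Half adherence roughly halves the counts. Because the interval is only recommended, the true number could be zero.

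**What the class does to the estimate.** Biopsies are scheduled only at Visits 3c and 9, so MAR imputation has little beyond baseline and arm to use, and it returns the complete-case ANCOVA on average. In 4000 simulated trials with 31 per arm, the mean difference between the two log estimates was at most 0.0005 in size. The last column above shows the opposite extreme: every affected tralokinumab subject is imputed from placebo and contributes no effect, giving 3.5^(1−p). The largest move is a factor of 3.5/2.93 = 1.19, against the confidence factor of 2.40.

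**What a reader will see.** The primary and out-of-window analyses differ only in the out-of-window biopsies. If numbers analysed are shown by arm for both, as is usual, the difference gives the total by arm. SAP 4.1 lists all data by treatment and subject, SAP 4.2.4 lists the biopsy counts, SAP 4.2.6.3 lists the exacerbations, and SAP 4.2.2 summarises days of systemic steroids for exacerbations up to Week 12.

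**The case for a change.** The best case for a change is that the SAP sets out to separate biopsy-related from other missingness, and its definition then merges them for this group. The protocol promises several assumptions, while the imputation applies only MAR here. A separate class, with one run on the late value and one placebo-based bound, would need only wording and steroid dates that SAP 3.2.3.5 already uses. It would have to be fixed before unblinding.

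Part of this stands. The procedural rationale does not describe an exacerbation delay, the steroid cause is not named, and there is no dedicated count by arm.

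The remedy adds little, however. The run on late values largely repeats the out-of-window analysis. The placebo-based run would discard observed values in subjects who have not dropped out and may still be on treatment, which is debatable when SAP 4.1 includes data irrespective of adherence. The class would also have to be inferred from steroid dates, since the documents describe no field for the reason for delay. The promised range of assumptions is met across the planned analyses together: MAR, placebo-based imputation for treatment-related dropouts, and observed late values.

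Keeping late biopsies out of the primary analysis is a fair trade-off. Protocol 3.8 equates 16 weeks with five half-lives, so one half-life is 112/5 = 22.4 days. With first-order decline, exposure on days 100 to 127 is 0.5^(15/22.4) = 63% down to 0.5^(42/22.4) = 27% of the day 85 level.

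**Conclusion.** No change to the plan is needed. Read literally, one sensitivity analysis treats a late but observed biopsy as a failed one. This is a loose definition with no shown effect on any conclusion. The primary estimate is the same whichever class is used, the imputation would be MAR under either label, and the observed values are used in an analysis planned in the same SAP section.

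The size rests on assumed rates of 0.5 to 2 exacerbations per year and full adherence: 1.2 to 4.4 of 31 subjects per arm, with a bound of 3.34 to 2.93 on a 3.5-fold effect. The out-of-window analysis helps only if the delayed biopsy is actually taken. Where it is never taken, the value is truly unobserved and MAR is the only treatment, but the same bound shows that the effect stays small against the trial's precision.

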## **1.3** Number of subjects

The study is powered to show a reduction in airway submucosal eosinophils, from baseline to Week 12 (Visit 9) for tralokinumab, versus placebo in the overall study population.

The sample size is based on the primary endpoint; change from baseline to Week 12 (Visit 9) in airway submucosal eosinophils. Given an assumed deviation of the log values in the 2 treatment groups are 1.62 and 1.82 it is estimated that 31 subjects in each treatment arm will be sufficient to achieve at least 80% power to detect a 3.5-fold difference versus placebo using a two-sided test at 5% significance level. It is assumed that a non-neglectable proportion of the subjects will not have an evaluable primary endpoint value due to failed biopsies. To account for this, 40 subjects will be randomized in each treatment arm.

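### The protocol promises imputation under a range of missing-data assumptions; the SAP gives one scenario, with missing Week 12 biopsies taken as MAR and a placebo-based step written for event counts instead of the log ratio

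*SAP*

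**What the plan says.** Protocol 8.5.5 states: "We cannot rule out that there is a relationship between unobserved values and the likelihood of data being missing". It therefore undertakes that "the effect of missing data will be assessed using multiple imputations and a range of assumptions for the missing data", and leaves the details to the SAP.

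SAP 4.1.1 describes one multiple-imputation analysis with three rules:

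- **Biopsy-related missingness.** "In the sensitivity analysis implemented by multiple imputation (MI), biopsy-related missingness will be imputed assuming MAR". A subject falls in this class, a "biopsy-related missing outcome if the biopsy outcome is missing at Week 12, but other Week 12 data was collected for the subject".
- **Treatment-related dropout on tralokinumab.** The reasons listed are adverse events, death, study-specific stopping criteria and severe non-compliance. These values are "imputed based on the expected event rate in the placebo arm".
- **All other dropouts.** MAR.

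The next paragraph of 4.1.1 says the data are log-transformed, that "the ratio of each scheduled visit to baseline visit will be the variable of interest for imputation", and that SAS monotone regression is used.

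The other sensitivity analyses in 4.1.1 are ANCOVA on the untransformed change, two rank ANCOVAs, exclusion of zero values, and an analysis "keeping the subjects with the week 12 records falling outside of the week 12 window". SAP 4.2.4 requires both biopsies for the primary analysis, so it is a complete-case ANCOVA. SAP 1.3 explains the increase from 31 to 40 per arm by subjects who "will not have an evaluable primary endpoint value due to failed biopsies".

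**The concern.** The two documents do not match. The protocol raises informative missingness and promises more than one assumption. The SAP takes the largest expected source of loss, failed or absent Week 12 biopsies, as non-informative and never tests that. SAP Section 1 says departures from the protocol are described in Section 6, but Section 6 does not record this narrowing.

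The MAR class is also wider than its name suggests, because it is defined by the presence of other Week 12 data and not by why the biopsy is absent. Two routes show this:

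- A tralokinumab subject who stops study drug for an adverse event, stays in the study and has Week 12 data but no biopsy is imputed as MAR, despite a treatment-related reason for stopping.
- Protocol 5.1.12 recommends six stable weeks between systemic steroids for an exacerbation and the end-of-treatment bronchoscopy. The SAP's Week 12 window closes on day 99, so a last steroid dose after day 57 (99 − 42) pushes the biopsy out of window. If it is then never done, it is imputed as MAR, although an exacerbation is plausibly related to airway inflammation.

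The one non-MAR step cannot be programmed as written. It speaks of counts and an event rate, with undefined symbols, while the imputed variable is a continuous log ratio.

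At stake is whether the trial can say if its primary result depends on the subjects without a Week 12 biopsy.

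**Working it through.** **Inputs.** Log-scale SDs 1.62 and 1.82, 3.5-fold effect, two-sided 5%, 31 evaluable and 40 randomised per arm, smallest significant difference 2.4-fold (Protocol 8.2). Biopsies are taken only at baseline and Week 12 (Protocol Table 1).

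**The plan's own figures reproduce.**
- Pooled SD = √((1.62² + 1.82²)/2) = 1.723; ln 3.5 = 1.253.
- SE at 31 per arm = 1.723 × √(2/31) = 0.438. Noncentral-t power is 80.4%.
- Smallest significant ratio = exp(t(0.975, 60 df) × 0.438) = 2.40.
- Allowance: 40 − 31 = 9 per arm, or 9/40 = 22.5%. The documents state no rate; this is the subtraction.

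**What the planned imputation does.** Simulation used 1,000 trials per setting, 40 per arm, 9 missing per arm and 50 imputations, with SD 1.82 assigned to tralokinumab and 1.62 to placebo. The baseline correlation of −0.25 is assumed. Treatment and log baseline are the predictors, since the SAP names no auxiliary variables for the Week 12 imputation. The number k of tralokinumab losses that are treatment-related dropouts is assumed, because the documents give no split.

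| k imputed from placebo | Planned MI | Complete case |
|---|---|---|
| 0 | 3.52 | 3.51 |
| 1 | 3.40 | 3.51 |
| 2 | 3.27 | 3.48 |
| 4 | 3.05 | 3.45 |
| 9 | 2.65 | 3.52 |

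At k = 0 the two estimates correlate at 0.997. A separate simulation without baseline correlation gave 3.54 for both methods, with power of 80% (MI) and 81% (complete case). The imputation and analysis models share the same predictors and there is no intermediate biopsy, so MAR imputation has nothing to add.

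**What it misses.** Let m of the 40 tralokinumab subjects be missing and without benefit, with 3.5-fold in the rest. The all-randomised effect is 3.5^((40−m)/40):
- m = 3: 3.5^0.925 = 3.19
- m = 5: 3.5^0.875 = 2.99
- m = 9: 3.5^0.775 = 2.64

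In simulation with k = 0, the planned MI gave 3.49, 3.50 and 3.58 in these settings.

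**What a delta series would show.** Shifting the log ratios imputed for all 9 missing tralokinumab subjects by 0, 25, 50, 75 and 100% of ln 3.5 gave 3.49, 3.26, 3.03, 2.83 and 2.63-fold, with 81, 77, 71, 64 and 58% of trials significant. Other calculations of the full-effect case gave 59% (analytic), 62% (simulated, all 9 imputed from placebo) and about 64% (simulated full shift), so 58 to 64% is a fair range.

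**Tipping point, holding the complete-case SE fixed.** Significance is lost when the 9 missing tralokinumab values exceed the MAR prediction by a factor of exp((ln observed − ln 2.40)/0.225). For observed effects of 2.5, 3 and 3.5-fold this is 1.2, 2.7 and 5.4.

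**The case against.** The strongest reply has five parts.

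- **The detail was delegated.** The protocol names neither a delta adjustment nor a tipping point. The SAP does mix assumptions by reason, and this is a phase 2 mechanistic study with nominal p-values. That is true, but one mixed scenario is still a single result. It does not show how the conclusion changes as the assumption changes.
- **Procedural biopsy failure is probably uninformative.** This is reasonable for many specimens. It is strongest where the baseline specimen was unusable: Table 1 footnote xix and Protocol 8.5.1 indicate that such subjects are unlikely to have a second biopsy, and that loss cannot depend on treatment response. It does not cover everything the SAP's definition sweeps in. The out-of-window analysis recovers early or late biopsies but tests no assumption about absent ones.
- **The size is assumed.** The 9 of 40 is a subtraction, some of those losses will be baseline failures, and zero benefit is a strong assumption. This stands as a limit on the figures. The planned MI also moves once several dropouts are treatment-related (3.05-fold at four).
- **The count wording is carried over and easily read.** Possibly, but the placebo-based draw still has to be written down before unblinding.
- **A delta series capped at the full effect may find no tipping point.** At an observed 3.5-fold the tip needs a factor of 5.4, beyond the cap. That would be a useful finding of robustness. Weaker results do tip within the cap: setting observed^0.775 = 2.40 gives exp(0.875/0.775) ≈ 3.1, so significant effects below about 3.1-fold would lose significance before the full shift.

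**Conclusion.** The concern holds. The SAP does not deliver the range of assumptions in Protocol 8.5.5, does not record that change, and words its only non-MAR step for a different kind of endpoint. When few tralokinumab losses are treatment-related dropouts, the planned MI almost duplicates the complete-case analysis and cannot answer the question the protocol raises. With 9 of 40 missing per arm and 3.5-fold in observed subjects, the undetected attenuation runs from 3.19-fold (3 missing without benefit) to 2.64-fold (all 9, an illustrative worst case and not an expectation). These sizes rest on an assumed number and mix of missing subjects. The primary analysis and the sample size are not in question. This should be corrected before unblinding.

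**What to change.** In SAP 4.1.1:

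1. Keep the MAR imputation as the anchor.
2. Restate the placebo-based step as a draw of ln(Week 12/baseline) from the placebo-arm regression on log baseline, and remove the count and event-rate wording.
3. Add a delta series to the same imputation for missing Week 12 tralokinumab biopsies, including those classed as biopsy-related. Shift the imputed log ratios upward from 0 to the full estimated effect, for example in quarters. Report the estimate and interval at each step, and where significance is lost or that it is not lost within the range.
4. Losses caused by an unevaluable baseline specimen may stay MAR.
5. If the sponsor prefers a narrower set of assumptions, record and justify that in Section 6.

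The cost is SAP wording, a loop around the imputation already planned and a little more output. No new data are needed.

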# 4.2 Analysis methods

### 4.2.1 Subject disposition, demography data and subjects characteristics

Subject disposition will be summarized using the All subjects analysis set.

The number of enrolled subjects will be summarized. The number and percentage of subjects within each treatment group will be presented by the following categories; randomized, not randomized (and reason), received IP, did not receive IP (and reason), completed treatment, discontinued treatment (and reason), completed study, and discontinued study (including reason).

The number and percentage of subjects, who discontinued IP, but remained in the study will be presented by treatment group and will also be listed.

Demographic data such as age, gender, ethnicity and race will be summarized by treatment group for the FAS.

Various baseline characteristics will also be summarized by treatment for the FAS. These include medical, surgical and respiratory disease histories, asthma related events in the past 12 months, weight, height and BMI, use of nicotine (never/ former/ current), asthma duration (defined as date of informed consent – date of diagnosis), age at onset of asthma (defined as date of diagnosis – date of birth), asthma medications (using fluticasone as reference medication), the number of asthma exacerbations in the previous 12 months and number of asthma exacerbations in the previous 12 months.

Medical and surgical histories will be summarized by MedDRA Preferred Term (PT) within the System Organ Class (SOC) level of MedDRA version 20.0.

